Glycemic variability (GV), which refers to daily glucose fluctuations, including preprandial, postprandial glycemia, and hypoglycemic episodes, could be associated with an increase in oxidative stress and the development of microvascular complications in Type 2 Diabetes (T2D). Although SGLT2 inhibitors have been shown to reduce GV, there is no evidence regarding their effect in newly diagnosed T2D patients when used at the initiation of pharmacological therapy, nor regarding their impact on oxidative stress.

Main objective: To evaluate the effect of dual therapy with Dapagliflozin + Metformin (DAPA/MET) versus Metformin monotherapy (MET) over 12 weeks on GV in patients with T2D.

Secondary objectives: To evaluate the effects on HbA1c, insulin, plasma antioxidant capacity, body composition, and cardiometabolic risk factors.

Hypothesis: The reduction in glycemic variability (measured using the mean amplitude of glycemic excursions, MAGE) will be greater in patients receiving dual therapy with Dapagliflozin + Metformin compared to those receiving Metformin monotherapy.

Methods: 88 patients with T2D without catabolic symptoms or complications, with HbA1c >7.5% and <12% and BMI >25 kg/m² will be included. Patients will be randomized 1:1 to receive Dapagliflozin 10 mg/day + Metformin 2000 mg/day (n=44) or Metformin 2000 mg/day (n=44). GV will be measured with the iPro™ CGM system (Medtronic) at baseline and the end of the 12 weeks of treatment.

Statistical analysis: The primary dependent variable will be MAGE as a marker of GV. Other variables such as HbA1c, serum insulin, plasma antioxidant capacity, VCAM-1, and adiponectin will be analyzed. Change deltas will be calculated for each group and compared using ANCOVA. A p-value ≤0.05 will be considered significant. All analyses will be performed with SPSS 20.0.

Background

There is growing evidence regarding the beneficial effects of sustained intensive glycemic control on the incidence and progression of complications in T1D and T2D [1]. HbA1c has been the main marker used to define glycemic control because it provides an average of glycemia in the 2 or 3 months before its measurement, with the American Diabetes Association recommending that HbA1c levels be maintained between 6.5% and <8%, depending on the individual characteristics of each patient [2]. Although HbA1c is a standardized, validated, and evidence-based marker, it is not useful for evaluating glycemic fluctuations over short periods [1].

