HbA1c reflects the mean glucose concentration over the last 8 to 12 weeks. It is well documented that elevated HbA1c levels are associated with an increased risk of diabetes complications. However, evidence has shown that glycemic variability, particularly MAGE, is associated with greater vascular endothelial dysfunction and oxidative stress, consequently increasing the risk of developing retinopathy, nephropathy, and coronary artery disease. A frequently used measure of GV is MAGE, which reflects the mean of the differences between consecutive peaks and nadirs of blood glucose concentrations and is therefore independent of the mean glucose level [47]. Correcting GV is currently considered a clinical objective to reduce average glycemia and determine its direct effects on vascular complications in diabetes. Sodium-glucose cotransporter type 2 inhibitors have been shown to be effective in improving glycemic control, in terms of fasting glycemia, glycated hemoglobin, and glycemic variability determined by MAGE. However, the evidence primarily considers their use in Type 2 Diabetes patients diagnosed more than 5 years prior and previously treated with other pharmacological regimens, including insulin. Therefore, the effect of SGLT2i on glycemic variability and oxidative stress when used in patients with a recent diagnosis of Type 2 Diabetes is unknown.

10. Justification

Type 2 Diabetes is one of the most prevalent chronic diseases worldwide and constitutes the eighth leading cause of death and disability due to its micro and macrovascular complications. Chronic hyperglycemia, through the production of advanced glycation end products, induces a proinflammatory cascade involving mainly Interleukin 6, Tumor Necrosis Factor-alpha, and the formation of free radicals, such as superoxide and hydrogen peroxide. This generates a state of oxidative and mitochondrial stress, causing irreversible damage to cell membranes and interfering with various cellular signaling pathways, representing the main pathophysiological mechanism for the development of microvascular complications. For this reason, the current treatment of Diabetes focuses primarily on reducing exposure to hyperglycemia, and intensive glycemic control has been shown to decrease the risk of microvascular complications, especially if implemented early after diagnosis.

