However, most pivotal studies on intensive glycemic control predate the existence of medications such as SGLT2 inhibitors and GLP-1 agonists. Glycated hemoglobin (HbA1c) is the most widely used standardized marker for evaluating glycemic control, as it reflects the average glycemia over the last 3 months. However, it does not detect short-term glucose fluctuations or hypoglycemic episodes. Glycemic variability (GV), which refers to daily glucose fluctuations including preprandial, postprandial glycemia, and hypoglycemic episodes, could be associated with increased oxidative stress and the development of microvascular complications in Type 2

Diabetes (T2D). There is increasing information about the reduction in the risk of microvascular complications when decreasing glycemic variability is considered a treatment goal in both Type 1 and Type 2 Diabetes. SGLT2 inhibitors have demonstrated reduced GV and their beneficial cardiovascular and renal effects are now well known. Although the American Diabetes Association recommends their use in concomitant therapy with Metformin as a second line in patients not meeting targets with monotherapy and those with high risk of cardiovascular disease, chronic kidney disease, and/or heart failure, clinical endocrinologists are increasingly inclined to initiate T2D treatment with dual therapy including Metformin and an SGLT2i or a GLP-1 agonist when HbA1c at diagnosis is $>7.5\%$ and $\leq 9\%$, and in patients with HbA1c $>9\%$ without classic diabetes symptoms. Understanding the effect of SGLT2i on glycemic variability and markers of oxidative stress when used early in the diagnosis of Diabetes would allow establishing a line of research on their effect in reducing the risk of microvascular complications, thereby having a positive impact on the global burden of the disease.

Hypothesis

The reduction in glycemic variability (measured using the mean amplitude of glycemic excursions, MAGE) will be greater in patients receiving dual therapy with Dapagliflozin + Metformin compared to patients receiving Metformin monotherapy.

Objectives

Main Objective

To evaluate the effect of dual therapy of Dapagliflozin + Metformin (DAPA/MET) versus Metformin monotherapy (MET) on GV in patients with T2D after 12 weeks of treatment.

Specific Objectives

- To compare the effect of dual therapy of Dapagliflozin + Metformin versus Metformin monotherapy on HbA1c levels (%).

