Definition of Follow-up Variables

- **Primary Variable:** Change from baseline in GV (MAGE) in mg/dL after 12 weeks of treatment between the DAPA+ MET group versus the MET monotherapy group.
- **Secondary Variables:**
 - Change from baseline (absolute difference) in HbA1c levels (%) after 12 weeks of treatment between the DAPA + MET group versus the MET monotherapy group.
 - Change from baseline (total difference) in insulin levels (μ U/mL) after 12 weeks of treatment between the DAPA + MET group versus the MET monotherapy group.
 - Change from baseline (absolute difference) in oxidative stress measurement (total antioxidant capacity) after 12 weeks of treatment between the DAPA + MET group versus the MET monotherapy group.
 - Change from baseline (total difference) in the measurement of inflammation biomarkers (VCAM-1 and adiponectin) after 12 weeks of treatment between the DAPA + MET group versus the MET monotherapy group.
 - Change from baseline (absolute difference) in body fat quantification after 12 weeks of treatment between the DAPA + MET group versus the MET monotherapy group.
 - Change from baseline (total difference) in the parameters of cardio-metabolic risk factors (weight (kg), total cholesterol (mg/dL), HDL (mg/dL), LDLc (mg/dL), albuminuria (mg/mg creatinine), and blood pressure (mmHg)) after 12 weeks of treatment between the DAPA + MET group versus the MET monotherapy group.

Methods for Data Collection

Electronic Record containing the clinical history collected via telemedicine (Phone call/Videocall, Whatsapp, Teams, Zoom or Google Forms), information gathered at each visit, notes containing patient physical examinations, physical activity questionnaires answered via telemedicine (Phone call/Videocall, Whatsapp, Teams, Zoom or Google Forms), Nutrition notes collected via telemedicine (Phone call/Videocall, Whatsapp, Teams or Zoom), and laboratory results. Patients will only be identified by their initials, date of birth, and the internal protocol folio number.

Monitoring and Auditing Procedures During Study Development

Not applicable

Criteria for Failure and Success

- **Failure:** No decrease in GV in the DAPA + MET group compared to the MET monotherapy group.
- **Success:** A decrease in GV in the DAPA+ MET group compared to the MET monotherapy group.

Sample Size

The sample size was determined using the difference of means formula:

$$n = (Z\alpha / 2 + Z\beta)^2 * 2 * \sigma^2 / d^2,$$

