A reduction in glucose variability from 4.85 to 2.2 was estimated with an expected standard deviation of 2.8 in the MAGE index (values based on the study by R. R. Henry et al., "Effects of Dapagliflozin on 24-Hour Glycemic Control in Patients with Type 2 Diabetes: A Randomized Controlled Trial," *Diabetes Technol. Ther.*, vol. 20, no. 11, pp. 715–724, Nov. 2018.), with an alpha value of 0.05 and a power of 0.80, resulting in a sample size of 88 subjects, with 44 subjects in each treatment group. No adjustments were included in the sample size calculation to estimate the subjects required for the estimated differences in secondary variables.

Description of techniques, devices, and/or instruments to be used (Including special mechanical, electronic, cybernetic equipment)

Continuous glucose monitoring will be performed using the iPro™2 Continuous glucose monitor, from Medtronic®, to determine the MAGE value as follows:

- **Calculation of Mean Amplitude of Glucose Excursion (MAGE):**
 - In the first step, all local maximum/minimum values are determined.
 - The next step is an evaluation of maximum/minimum pairs against the standard deviation (SD).
 - If the difference from minimum to maximum is greater than the SD, this variation from the mean measurement is retained.
 - If the local maximum/minimum is less than 1 SD, it is excluded from further calculations.
 - These channels are retained and summed to achieve the MAGE
- Glycated hemoglobin (HbA1c) will be measured using HPLC (Variant II Turbo, Biorad).
- Insulin levels will be measured with Access-2 equipment (Beckman Coulter, Inc.).
- Oxidative stress will be measured with the BioAssay Systems antioxidant assay kit (DTAC-

100) (QuantiChrom Antioxidant Assay Kit) (BioAssay Systems).

- VCAM-1 will be measured using ELISA kits (Merck Millipore, USA).
- Adiponectin measured using ELISA kits (Merck Millipore, USA).
- Body fat quantification by bioelectrical impedance with the Jawon scale, model⁵ IOI 353 - JMW160.
- Anthropometric variables will be measured using standardized techniques; these include height, weight, waist, and hip circumferences.
- BMI will be calculated using the equation: weight / height² (kg/m²).
- Blood pressure will be measured considering the mean of two determinations after sitting for at least 5 minutes.
- Mean arterial pressure (MAP) will be calculated with the formula: (systolic blood pressure * 0.33) + (diastolic blood pressure * 0.66).

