- Change from baseline (total difference) in the measurement of inflammation biomarkers (VCAM-1 and adiponectin) after 12 weeks of treatment between the DAPA + MET group versus the MET monotherapy group.
- Change from baseline (absolute difference) in body fat quantification after 12 weeks of treatment between the DAPA + MET group versus the MET monotherapy group.
- Change from baseline (total difference) in the parameters of cardio-metabolic risk factors (weight (kg), total cholesterol (mg/dL), HDL (mg/dL), LDLc (mg/dL), albuminuria (mg/mg creatinine), and blood pressure (mmHg)) after 12 weeks of treatment between the DAPA + MET group versus the MET monotherapy group.

Methods to be used to contact patients

Personal contact data such as landline and mobile phone numbers, email address will be obtained via Phone call/Videocall, Whatsapp, Teams, Zoom, or Google Forms. Due to the SARS-CoV-2 pandemic, investigators will conduct home visits and/or collect data and hold medical consultations via Phone call/Videocall, Whatsapp, Teams, Zoom, or Google Forms.

Statistical Analysis (Description of the information processing and presentation plan. Include justification for the statistical tests to be used)

Stratified randomization in both groups to balance patient types and control potential bias. The normality of variables will be analyzed using the Kolmogorov-Smirnov test. According to the distribution of variables, they will be expressed as mean and standard deviation (SD) or median and interquartile range (IQR) for normally or skewed distributed variables, respectively. GV will be determined using the MAGE index. Comparison between the two groups will be evaluated using ANCOVA. A p-value based on two-tailed tests ≤ 0.05 will be considered significant. All analyses will be performed with SPSS 20.0 (Chicago, IL). Patients experiencing an acute stress event during the study will be excluded from the analysis due to the impact on GV.

Justification of sample size (include study power and the p-value considered significant)

The sample size was determined using the difference of means formula:

$$n = (Z\alpha / 2 + Z\beta)^2 * 2 * \sigma^2 / d^2,$$

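### The only step-by-step rule for the primary endpoint, MAGE, ends in a sum of excursions and never divides by their number

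*Protocol*

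**What the plan says.** Under Definition of Follow-up Variables, and again in section 39, the primary variable is "Change from baseline in GV (MAGE) in mg/dL after 12 weeks of treatment", compared between the two groups. The protocol's section on techniques, devices and instruments then sets out how MAGE is obtained from the iPro2 trace:

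1. Find all local maxima and minima.
2. Compare maximum/minimum pairs with the standard deviation.
3. Keep a pair if its difference exceeds 1 SD and drop it otherwise.
4. "These channels are retained and summed to achieve the MAGE".

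The next item in that section is the HbA1c assay, so the rule stops at the sum.

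Elsewhere the protocol describes a mean. The heading over these steps expands the acronym as a mean amplitude. The Hypothesis, in the Summary and in the main text, speaks of glycemic variability "measured using the mean amplitude of glycemic excursions, MAGE". Section 9 (Problem Definition) refers to "MAGE, which reflects the mean of the differences between consecutive peaks and nadirs of blood glucose concentrations".

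The protocol's Statistical Analysis section adds only this: "GV will be determined using the MAGE index". The SAP describes 7-day CGM recordings at baseline and week 12 and gives no formula for MAGE.

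**The concern.** A primary endpoint should be computable from its written rule. Here the written rule and the name of the index lead to different quantities. The two differ by more than a fixed scale factor. The multiplier is the number of retained excursions, which can vary between patients and between the two recordings of one patient. A change from baseline in the sum therefore mixes a change in how large the excursions are with a change in how many there are. The hypothesis concerns only the first of these. The protocol also defines trial success by a decrease in glycemic variability relative to metformin alone, so the definition of the index feeds directly into the main conclusion.

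**Working it through.** **Does anything else in the documents supply the division?**

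| Place | What it gives |
|---|---|
| Protocol, techniques section, list heading | Calls the index a mean amplitude |
| Protocol, techniques section, last step | Sum of what is retained, no division |
| Protocol, Summary and Hypothesis | Expands the acronym as a mean amplitude |
| Protocol, section 9 | Mean of peak-to-nadir differences |
| Protocol, Follow-up Variables and section 39 | Name and unit (mg/dL) only |
| Protocol, Statistical Analysis | Name of the index only |
| SAP | No formula, no MAGE value |

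The unit does not decide the matter, because a sum of amplitudes is also in mg/dL. The sample-size inputs do not decide it either. They run from 4.85 to 2.2 with no unit. The difference, 4.85 − 2.2 = 2.65, does not match the 15.3 mg/dL fall in MAGE that the Background quotes from the source study, so the scale of the index cannot be read from them. No other step-by-step rule exists.

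**Sum against mean.** Let *n* be the number of retained excursions and *m* their mean amplitude. The rule as written gives *S* = *n* × *m*, whereas the index as named is *m* = *S* / *n*.

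Hold *m* fixed and assume a starting point of 3 retained excursions a day:

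- 3 to 4 a day: 4/3 − 1 = +33.3% in *S*, 0% in *m*.
- 3 to 2 a day: 2/3 − 1 = −33.3% in *S*, 0% in *m*.
- Over 7 days the percentages are the same: 28/21 − 1 = +33.3% and 14/21 − 1 = −33.3%.

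These percentages do not depend on the amplitude, or on whether the sum is taken per day or over the recording.

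**The direction can reverse.** Assume 21 retained excursions of 90 mg/dL at baseline and 28 of 80 mg/dL at week 12:

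- Sum: 21 × 90 = 1890, then 28 × 80 = 2240, an apparent worsening.
- Mean: 90, then 80, an improvement.

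**Recording length.** This applies only if one sum is taken over the whole recording, with a constant excursion rate and an unchanged SD threshold. In that case 6 recorded days out of 7 give 6/7 − 1 = −14.3% in *S* and no change in *m*.

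The counts, the amplitudes and the lost day are assumptions, because the documents report none of them. The identity *S* = *n* × *m* is not an assumption.

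**The case against.** The strongest reply is that the documents largely answer the question themselves. The list is titled as a mean amplitude and section 9 describes a mean, so combining the 1 SD retention rule with that description gives the usual index. A sum is also the numerator of a mean, so the last step may simply be unfinished. Its wording looks like a drafting or translation slip: it speaks of channels, a term the procedure never defines. The heading and the two hypothesis statements only expand the acronym, which leaves section 9 as the one independent description. The percentages rest on assumed counts. The recording-length example needs several unstated conditions, while the plan sets 7 days for both groups at both times and the SAP reports no shortened recordings. Finally, the SAP describes the trial in the past tense, so a protocol edit cannot change its conduct.

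Much of this stands. The intended index is very probably the mean, no effect on the result is shown, and the recording-length example is hypothetical. What remains is that the only executable rule for the primary variable gives a different quantity when executed, and a reader must set aside or complete its last step to reach the intended one. A slip explains the error without removing it. That the trial has been run makes a statement of what was actually computed the most useful part of the correction.

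**Conclusion.** The concern holds, and the rule should be corrected. As written, the protocol's rule for the primary endpoint produces the count of retained excursions times their mean amplitude, against its own heading, the Hypothesis and section 9, and the SAP does not repair it. At constant amplitude, a change of one excursion a day from an assumed 3 moves the written quantity by 33% in either direction and leaves the mean where it was. The conclusion concerns the written rule. It rests on reading the retained items as the excursions that pass the 1 SD test, which the preceding steps support. It does not say that a sum was used in the analysis.

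There is also a related gap in the specification. The rule does not say whether the SD threshold and the final value are taken per day or over the whole trace. It points only partly, through its minimum-to-maximum comparison, to which direction of excursion counts.

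**What to change.** Replace the last step of the rule with:

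> MAGE is the arithmetic mean of the retained excursions (amplitude greater than 1 SD), that is, their sum divided by their number, in mg/dL.

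Put the same sentence in the SAP, applying to both CGM periods. Beside it, state the algorithm or software actually used, whether the SD and the mean were taken per day or over the whole trace, and whether upward, downward or both kinds of excursion were counted.

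The cost is one sentence in each document plus that short statement. If the check shows that a sum was computed, MAGE must be recomputed from the stored CGM traces and the primary comparison rerun. If a mean was computed, no reanalysis is needed on this account.
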